# 7 Milestones

Planned duration of recruitment period (i.e. FPFV - LPFV ): 18 month

End of trial is defined as LPLV.

#### For United Kingdom:

Planned date for LPLV: 27-Nov-2018

#### **Recruitment:**

Recruitment will be monitored on an ongoing basis by the sponsor. Prior to the initiation visit all trial sites should have a recruitments mitigation plan in place detailing how many subjects they can recruit within a certain period. If a trial site has not enrolled the number of subjects according to the recruitment mitigation plan, the remaining subjects may be reallocated.

The screening and randomisation rate will be followed closely via the interactive voice/web response system (IV/WRS) in order to estimate when to stop screening. All investigators will be notified immediately when the recruitment periods ends, after which no further subjects may be screened and the IV/WRS will be closed for further screening. All subjects included in the screening period and eligible for randomisation can be randomised.

#### **Trial registration:**

Information of the trial will be disclosed at clinicaltrials.gov and novonordisk-trials.com. According to the Novo Nordisk Code of Conduct for Clinical Trial Disclosure , it will also be disclosed according to other applicable requirements such as those of the International Committee of Medical Journal Editors (ICMJE) , the Food and Drug Administration Amendment Act (FDAAA) , European Commission Requirements  and other relevant recommendations or regulations. If a subject requests to be included in the trial via the Novo Nordisk e-mail contact at these web sites, Novo Nordisk may disclose the investigator's contact details to the subject. As a result of increasing requirements for transparency, some countries require public disclosure of investigator names and their affiliations.

CONFIDENTIAL

Date: Version: Status: Page: 07 May 2015 **Novo Nordisk** 2.0 Final 48 of 141

# 8 Methods and assessments

# 8.1 Visit procedures

Throughout the trial the investigator should ensure working in accordance with (ICH GCP) $\frac{1}{2}$  and local regulations. The investigator must ensure that trial procedures are performed as described in the protocol. Any discrepancies will result in protocol and/or GCP deviations and the investigator must take appropriate action to avoid recurrence of the detected discrepancies.

The following sections describe the assessments and procedures that must be performed during this trial. The timing of the assessments and procedures are specified in the flow chart Section 2.

The investigator must keep a subject screening log, a subject identification code list and a subject enrolment log. The subject screening log and subject enrolment log may be combined in one list and may be generated from the IV/WRS.

In addition the investigator must keep a log of staff and delegations of task(s) at the site. The investigator must sign the log of staff and the delegation of task(s) at site at the time of delegation.

# 8.1.1 Informed consent

Before screening takes place, subjects must be provided with oral and written information about the trial and the procedures involved. Subjects will be fully informed, orally and in writing about their responsibilities and rights while participating in the trial, as well as about the possible advantages and disadvantages when participating in the trial. Subjects will have the opportunity to ask questions and have ample time to consider participation. The informed consent process may take place before the screening visit (Visit 1).

Subjects who wish to participate in the trial must sign and date the subject information/informed consent for the trial before any trial related procedures (see Section 18.2). All subjects must be provided with a copy of their own signed and dated informed consent form.

# 8.1.2 Screening

At screening (V1), subjects will be provided with a card stating that they are participating in a trial and giving contact address(es) and telephone number(s) of relevant trial site staff. Subjects should be instructed to return the card to the investigator at the last trial visit or to destroy the card after the last visit.

Each subject will be assigned a unique 6-digit subject number which will remain the same throughout the trial.

Protocol Trial ID: NN9828-4150 UTN: U1111-1154-7172 EudraCT no.: 2014-001215-39	Date: 07 May 2015   Version: 2.0   Status: Final   Page: 49 of 141	Novo Nordisk
--	--	--------------

## 8.1.3 Screening failures

If any inclusion criteria are answered no or any exclusion criteria are answered yes, the subject is a screening failure.

For screening failures the screening failure form in the electronic case report form (eCRF) must be completed with the reason for not continuing in the trial. Serious adverse events from screening failures must be transcribed by the investigator into the eCRF. Follow-up of serious adverse events (SAEs) must be carried out according to Section 12.3. A screening failure session must be made in the IV/WRS. The case book must be signed after all queries are closed.

#### 8.1.4 Re-screening/re-sampling

Re-sampling or re-screening is NOT allowed if the subject has failed one of the inclusion or exclusion criteria related to laboratory parameters.

However if the **tuberculosis screening test** at Visit 1 is inconclusive re-tests can be performed. The repeat test results must be available for evaluating the subject's eligibility before Visit 3.

#### 8.1.5 Investigator's assessment

It is the responsibility of the investigator or delegated staff to review the e-diaries, PROs, ECGs, eye examinations (fundoscopy/ fundus photography), laboratory reports etc. This must be documented with the investigator or delegated staff's dated signature either on the front page of the documents and/or in the subject's medical records. The signed documents must be retained at the investigator site as source documentation.

# 8.1.6 Missed visits and unscheduled visits

If a visit is missed every effort should be made to ensure information is collected at a telephone contact. Subjects will be invited for the next scheduled visit according to the visit schedule.

If the investigator asks to subject to have a test described in the protocol re- done (e.g extra blood sample if some of the blood sample values are out of range) this should be recorded as an unscheduled visit and an unscheduled visit form must be completed.

If the subject attends the clinic and some of the tests have to be re-scheduled (e.g. in a non-fasting state at a fasting visit) the re-scheduled tests should NOT be recorded as an unscheduled visit. In this case blood samples will have a different date of collection than the rest of the assessments. Likewise re-scheduling of the MMTT and dosing of NNC0114-0006/placebo should not be recorded as an unscheduled visit. Temporary discontinuation of trial product

A temporary discontinuation is when the subject temporarily discontinues trial product after randomisation see Section 6.5

Protocol	FIAL Date:	07 May 2015   Novo Nord	isk
Trial ID: NN9828-4150	Version:	2.0	
UTN: U1111-1154-7172	Status:	Final	
EudraCT no.: 2014-001215-39	Page:	50 of 141	

#### 8.1.7 Withdrawn subjects

If a subject is withdrawn from the trial during the treatment period (week 0-54), the investigator must aim to undertake procedures similar to those for Visit 63 as soon as possible and perform the safety follow up visit (Visit 90)  $15 \pm 1$  weeks after last dose of NNC0114-0006. Subjects will be instructed to use appropriate pregnancy prevention until 15 weeks after last dose of NNC0114-0006. The end-of-trial form must be completed, and final drug accountability must be performed even if the subject is not able to come to the trial site. A withdrawal session must be made in the IV/WRS. The case book must be signed after all queries have been closed.

If a subject is withdrawn from the trial during the observation period (week 55-80), the investigator must aim to undertake procedures similar to those for Visit 89 as soon as possible and the safety follow up visit (Visit 90)  $15 \pm 1$  weeks after last dose of NNC0114-0006. Subjects withdrawn 14 weeks or more after last dose of NNC0114-0006 should not attend Visit 90. The end-of-trial form must be completed. A withdrawal session must be made in the IV/WRS. The case book must be signed after all queries have been closed.

Additional follow-up of subjects due to adverse events (AEs) or pregnancy is described in Section 12.3 and 12.5.

If subjects fails to return for these visits or is unable to do so, every effort should be made by the investigator to contact him/her by phone or by sending appropriate correspondence (i.e., certified letter) that will become part of the investigators' file to record that efforts were made to reach the subject.

Although a subject is not obliged to give his/her reason(s) for withdrawing from a trial, the investigator must make a reasonable effort to ascertain the reason(s), while fully respecting the subject's rights. Where the reasons are obtained, the primary reason for not completing the trial must be specified on the end-of-trial form in the eCRF.

If new information becomes available which the safety committee at Novo Nordisk concludes would compromise the safety of the subjects, the trial will be permanently discontinued. In such cases, the subjects will still need follow-up visits as described above, i.e. at discontinuation and at 15 weeks  $\pm 1$  week after last dosage of NNC0114-0006 dosage for safety reasons.

#### 8.1.8 Fasting visits

The subject should attend selected visits fasting (see Section 2).

Fasting is defined as no food or drink intake for at least 6 hours, except water. Trial products and any medication which should be taken with or after a meal should be withheld on the day of the visit until blood sampling and body weight measurements have been performed.

Protocol		Date:	07 May 2015	Novo Nordisk
Trial ID: NN9828-4150	CONFIDENTIAL	Version:	2.0	
UTN: U1111-1154-7172	CONFIDENTIAL	Status:	Final	
EudraCT no.: 2014-001215-39		Page:	51 of 141	

If the subject is not fasting as required on days where fasting blood sampling should be drawn all blood samples (both fasting and non-fasting) must be re-scheduled within the visit window and the date for the fasting blood samples must be recorded in the eCRF. All other assessments can be performed even though the subject is not fasting. Re-scheduling of fasting blood samples is not considered as an unscheduled visit.

#### 8.2 Subject related information

The timing of the assessments is specified in the flow chart Section  $\underline{2}$ .

#### 8.2.1 Concomitant illness and medical history

A **concomitant illness** is any illness that is present at the start of the trial (i.e. at the screening visit (V1)) or found as a result of a screening procedure. The disease under investigation (T1DM) should not be entered as it is captured under diagnosis of diabetes.

**Medical history** is a medical event that the subject has experienced in the past. Only relevant medical history should be reported.

The information collected for concomitant illness and medical history should include diagnosis, date of onset and date of resolution or continuation, as applicable.

Any change to a concomitant illness should be recorded during the trial. A clinically significant worsening of a concomitant illness must be reported as an AE.

# 8.2.2 Concomitant medication

A **concomitant medication** is any medication, other than the NNC0114-0006, liraglutide and insulin, which is taken during the trial, including the screening and follow-up periods. Information on insulin treatment is recorded in diabetes treatment history see Section 8.2.7 and in the e-diary see Section 8.6.3.

Details of any concomitant medication must be recorded at the first visit. Changes in concomitant medication must be recorded at each visit as they occur.

The information collected for each concomitant medication includes trade name or generic name, start date and stop date or continuation.

If a change is due to an AE, then this must be reported according to Section 12. If the change influences the subject's eligibility to continue in the trial, the monitor must be informed.

For restrictions regarding concomitant medication, please refer to Section 5.3.

Protocol Trial ID: NIN0828 4150		Date:	07 May 2015	Novo Nordisk
UTN: U1111-1154-7172 EudraCT no.: 2014-001215-39	CONFIDENTIAL	Status: Page:	2.0 Final 52 of 141	

## 8.2.3 Smoking status

Details of smoking status must be recorded at the first visit. Smoking is defined as smoking at least one cigarette, cigar or pipe daily. The collected information should include whether or not the subject smokes or has smoked.

#### 8.2.4 Abuse of alcohol and/or drugs

Subject will be asked if he/she has a history of alcohol and/or drug abuse or is currently abusing alcohol and/or drugs. In case of a history of alcohol and/or drug abuse, duration of abuse in years and the year of end of abuse should be recorded in the eCRF.

#### 8.2.5 Demography

The following information has to be recorded:

- Date of birth, unless not permitted by local regulations
- Age
- Sex
- Race, unless not permitted by local regulations
- Ethnicity, unless not permitted by local regulations

#### 8.2.6 Diagnosis of diabetes

The following information has to be recorded:

• Date of diagnosis of T1DM

# 8.2.7 Diabetes treatment history

The following information has to be recorded:

- Start date of current diabetes treatment
- Number of severe hypoglycaemic episodes since diagnosis

#### 8.2.8 Family history of diabetes

The following information has to be recorded:

- Is there a family history of diabetes (Y/N)
- Indicate the relation to the subject
- Type of diabetes

## 8.2.9 Diabetes complications

The following information has to be recorded (Y/N):

CONFIDENTIAL

Date: Version: Status: Page: 07 May 2015 2.0 Final 53 of 141

- Diabetic retinopathy
- Diabetic neuropathy
- Diabetic nephropathy
- Other

#### 8.3 Assessments for efficacy

The timing of the assessments and procedures are specified in the flow chart Section 2.

#### 8.3.1 Mixed meal tolerance test

The subject will have a MMTT performed at certain visits, as outlined in Section  $\underline{2}$ .

#### Instructions prior to MMTT visits

The subject should be instructed to:

- Follow normal routine on the days prior to the MMTT visit regarding eating however the subject should attend the MMTT visit fasting
- Follow normal exercise and refrain from hard exercise (comparable to and exceeding 5 km running or weightlifting) 24 hours prior to the MMTT
- Minimise physical activity in the morning of the MMTT to the extent possible
- Refrain from intake of alcohol and use of medications that affect motility (i.e. prokinetics, anticholinergic, tricyclic antidepressants) 24 hours prior to the MMTT
- Not to take their basal insulin after 22.00 the evening before the MMTT visit
- Subjects who normally take basal insulin in the morning should bring their basal insulin to the MMTT
- Not to take any bolus insulin later than 2 hours prior to the MMTT
- Remember to bring their bolus insulin to the MMTT visits (to be given after MMTT)
- Take liraglutide/liraglutide placebo at the same time as usual both the day before the MMTT visit and on the day of the MMTT
- Remember to bring their liraglutide/liraglutide placebo to the MMTT visits, if applicable
- Remember to bring their BG meter provided for this trial
- Remember the importance of having BG on target

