#### 5.3.2 Liraglutide

Liraglutide and liraglutide placebo will be self-administered s.c. either in the abdomen, thigh or upper arm daily with a pen-injector around the same time of the day, when the most convenient time of the day has been chosen. The last dose of liraglutide will be administered at the day prior to the Visit 63 (week 54).

Liraglutide and insulin should not be injected in close physical proximity.

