# 2.23 Section 8.3.1 Mixed meal tolerance test

- Not to take their basal insulin after 22.00 the evening within 9 hours before the MMTT visit
  - Subjects who normally take basal insulin in the morning should bring their basal insulin to the MMTT *visit*
- Remember to bring their bolus insulin to the MMTT visits (to be given after *the* MMTT)
- Take liraglutide/liraglutide placebo at the same time as usual-both *on* the day before the MMTT visit and *as well as* on the day of the MMTT
- Remember the importance of having BG <del>on at</del> target

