
conducted 15 weeks  $\pm$  1 week after last dose of NNC0114-0006/placebo

2. Only for NNC0114-0006

required by local law. Austria: Urine-stick pregnancy test will be performed monthly. For Belgium: A monthly urine pregnancy test is mandatory for female subjects of 3. Blood sample at V63. A urine stick pregnancy test must be performed throughout the trial for females of childbearing potential if a menstrual period is missed or as

childbearing potential. Ireland: Urine-stick pregnancy test will be performed at all visits to the clinic.

4. The MMTT may be re-scheduled twice within 10 days

5. 4-point profile will be used for T-T-T

6. A fundoscopy/ fundus photography may be performed up to 2 weeks before or after V63 and up to 2 weeks before V89

7. PK sample for NNC0114-0006 (pre-dose and 1 hour sample after start of infusion)

8. Last dosing of NNC0114-0006/placebo

9. Last dosing of liraglutide/liraglutide placebo is the day prior to V63

CONFIDENTIAL

08 November 2016 2.0 Final 24 of 28

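### The protocol gives conflicting instructions on the same-day liraglutide dose at the week-54 meal test, and the SAP's dosing-gap analysis does not separate the two cases

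*Protocol*

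**What the plan says.** **Dosing on the test day.** The list of instructions before MMTT visits in Protocol Section 8.3.1 says "Take liraglutide/liraglutide placebo at the same time as usual both the day before the MMTT visit and on the day of the MMTT". That is the wording of protocol version 2.0. Amendment 2 (its Section 2.23) changed only the phrasing, shown in tracked form as "at the same time as usual-both *on* the day before the MMTT visit and *as well as* on the day of the MMTT". Dosing on the day stays, and no visit is excepted.

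**Final dose.** Section 5.3.2 places the last liraglutide dose on the day before Visit 63. Footnote 9 to the Visit 38 to 90 flow chart, carried through Amendment 3, agrees: "Last dosing of liraglutide/liraglutide placebo is the day prior to V63". Section 4.2.2.4, repeated in SAP Section 1.1.2.2, refers instead to a last liraglutide dose given at week 54.

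**Fasting visits.** MMTT visits are fasting visits: Section 8.3.1 has the bullet "however the subject should attend the MMTT visit fasting". For fasting visits, Section 8.1.8 names trial products, together with medication tied to a meal, and says that these "should be withheld on the day of the visit until blood sampling and body weight measurements have been performed".

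**Antibody samples.** Section 8.5.2.2 requires anti-drug antibody samples taken on treatment to precede that day's trial product. It schedules them at Visits 19, 31, 43 and 63, among others.

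**Analysis.** SAP Section 2.3 adds a sensitivity analysis that drops meal tests dated more than a day after the final liraglutide injection. It also adds an exploratory analysis with liraglutide concentration on the test date as a covariate, in the two liraglutide groups.

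**The concern.** The primary endpoint is the week-54 C-peptide AUC divided by the AUC at Visit 2, before any trial product. If some subjects inject shortly before the week-54 test and others do not, any acute effect of the drug on the test does not cancel in that ratio.

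The documents make such an effect plausible. Section 3.1 lists glucose-dependent insulin secretion and slower gastric emptying among the effects of liraglutide in healthy subjects and in type 2 diabetes. Section 8.3.1 itself keeps motility-affecting medication away from the test for 24 hours. Only the combination arm and the liraglutide-alone arm carry active drug, so variation in timing would act in two arms and not in placebo. What is at stake is uniform conditions at the test on which the trial is judged.

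**Working it through.** The plan states no figure on this point, so there is none to reproduce. The check is a comparison of the texts.

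**Step 1: which visits.** On-treatment MMTTs are at Visits 19, 31, 43 and 63 (weeks 12, 24, 36 and 54). Visit 2 precedes treatment; Visits 74 and 89 follow it.

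**Step 2: Visit 63, subject whose usual injection time is before the test.**

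| Source | Dose that morning before the test? |
|---|---|
| Section 8.3.1, as kept by Amendment 2 | Yes |
| Section 5.3.2 and footnote 9 | No; dosing ended the day before |
| Section 4.2.2.4 | Implies a last dose at week 54, no time of day |

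The first two rows cannot both be obeyed, and no section says which takes precedence.

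**Step 3: Visits 19, 31 and 43, same subject.** Section 8.3.1 has the dose taken at the usual time. If that comes before the antibody sample, Section 8.5.2.2 is broken. If Section 8.1.8 covers liraglutide, and if its reference to blood sampling includes the four hours of MMTT sampling, it is broken too. Both conditions are matters of reading: the clause about meals may qualify trial products as well as other medication, and liraglutide is not tied to meals.

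**Step 4: who is affected.** Section 5.3.2 lets the subject choose the time of day, and the MMTT starts in the morning. For an evening injector the same-day dose falls after the test, so exposure during the test is the same under every rule. The conflict bites only for those who inject before the test. Their share is not given.

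**Step 5: re-scheduled tests.** An MMTT may be moved by 1 to 10 days, up to twice. No passage says whether dosing continues until a re-scheduled week-54 test. This is a separate gap, and it can arise whatever the injection time.

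**Step 6: what the SAP analysis separates.** Counting by date, a same-day dose gives a gap of 0 days and a day-before dose a gap of 1 day. The exclusion applies above 1 day, so both stay in and are pooled. The rule addresses Step 5 but not Step 2.

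**Step 7: size.** If a fraction f of a liraglutide arm has dosed before the test, and that multiplies the AUC by (1 + d), the arm's mean log ratio moves by f × ln(1 + d). The documents give neither f nor d, nor the sign of d, so no figure is offered.

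**The case against.** **The Visit 63 text is specific and should prevail.** The Section 8.3.1 list serves every MMTT, including Visits 2, 74 and 89, when no liraglutide is due, so it has to be read with the dosing schedule. Other text fits a day-before last dose: the flow chart dispenses liraglutide at Visits 43, 49 and 55 but not 63, and protocol Section 17 ends the treatment period the day before the week-54 visit. This is a reasonable reading, but the protocol never states it and Section 4.2.2.4 points elsewhere. In the same list, the bullet on bringing the pen is limited to cases where it applies; the bullet on taking the dose is not.

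**Section 8.1.8 is ambiguous, and at Visit 63 it agrees with Section 5.3.2 that nothing is taken before sampling.** This stands. A reader might infer a three-way contradiction at Visit 63; the texts support one between Section 8.3.1 and the last-dose rule.

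**The pharmacological effect may be slight.** This stands. Section 3.1 says the insulin-secretion effect may be limited in type 1 diabetes, and no passage gives an effect of dose timing.

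**Exposure is measured already.** This stands in part. Liraglutide is sampled at Visit 63, but Section 8.5.3.4 allows the sample at any point in the visit. The concentration analysis is exploratory and does not identify when the dose was taken.

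**Conclusion.** Wrong as written, in a limited form. At the primary-endpoint visit the instruction to dose on the test day contradicts the stated last-dose day. At the three earlier on-treatment MMTT visits the same instruction contradicts the antibody-sampling rule for subjects who inject before the test and, on one reading, the fasting-visit rule. Exposure during the test can differ only in the two liraglutide arms and, for tests held on the visit day, only among subjects who inject before the test. The size of any effect on AUC is unknown and may be small.

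Two stronger readings are tempting. A reader might infer that both liraglutide arms are affected throughout, or that a definite part of the planned treatment effect is at risk. The documents support neither: injection time is free, and no timing effect or share of pre-test injectors is given. A reader might also infer that the repeated-measures model needs equal exposure at weeks 12, 24, 36 and 54. It does not. Treatment effects are visit-specific with unstructured covariance, and the observed week-54 contrast is with placebo at the same visit.

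**What to change.** **Protocol.** The sponsor must reconcile Sections 4.2.2.4, 5.3.2, 8.1.8, 8.3.1 (as amended) and 8.5.2.2 and flow-chart footnote 9, so that one consistent instruction applies at each MMTT visit and to re-scheduled tests. Which rule applies is for the sponsor to decide.

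**SAP.** Tabulate time since the last liraglutide or placebo dose at each MMTT, by arm. Add to the existing gap sensitivity analysis a version that separates same-day from day-before dosing. Use e-diary dose times if available: Sections 8.6.2 and 14.1 provide for them, but Amendment 2 edited Section 8.6.2 and its deletions are not visible in the text reviewed. SAP Section 3 also shows that insulin-dose data were transferred from the e-diary only in part. Confirm that liraglutide times were kept and transferred; otherwise use dose dates.

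**Cost.** A short protocol clarification, one derived variable, one table and one further sensitivity run. If times were kept and transferred, or dates suffice, no new data are needed.
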